| | To estimate the difference in physician-scored use experience between BrachyGel and standard vaginal packing. | Physician-scored use experience scored on a 4-point scale for periods 1 through 4 (e.g. fractions 2 through 5). |
| Study Population: | Adult women with locally advanced cervical cancer (FIGO Stages IB1-IVB) for whom brachytherapy boost is planned using intracavitary high-dose rate brachytherapy as part of definitive radiation therapy. | |
| Description of Sites/Facilities Enrolling Participants: | Participants will be enrolled at the University of Virginia and at the Allegheny Health Network | |
| Description of Study Intervention: | Participants will receive brachytherapy according to clinical care and will alternate between standard packing and BrachyGel packing. The order of alternation will vary between Arms A and B. | |
| Study Duration: | Accrual should be completed within 14 months and data collection and analysis will take after 12 additional months (total of 26 months). | |

| Participant Duration: | Each participant will receive 5 fractions of brachytherapy, each about |
|-----------------------|--|
| | 2-7 days apart, followed by a 30 day safety visit. |
| | |

Version Date: 11/16/2021

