7.2 Participant Discontinuation/Withdrawal

Participants are free to withdraw from participation in the study at any time upon request.

A participant's study treatment would be discontinued for the following reasons:

- Pregnancy
- Significant study intervention non-compliance
- Severe, CTCAE Grade ≥ 4 adverse event considered at least possibly related to the packing procedure
- Participant is unable to receive further brachytherapy due to an adverse event or a change in status (e.g. decline due to disease, change in goals of care, development of metastases).
- Participant decision to withdraw from study treatment and/or the study

The reason for participant discontinuation or withdrawal from study treatment will be recorded on the case report form. Participants that withdraw from study treatment only, will continue with study follow-up. Participants that withdraw from study treatment and study follow-up will not be contacted for any further study visits.

Version Date: 11/16/2021

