7.3 Procedures for Discontinuation of Study Intervention

Discontinuation from brachytherapy according to the study does not mean discontinuation from the study, and remaining study procedures should be completed as indicated by the study protocol. If a clinically significant finding is identified (including, but not limited to changes from baseline) after enrollment, the investigator or qualified designee will determine if any change in participant management is needed. Any new clinically relevant finding will be reported as an adverse event (AE).

The data to be collected and procedures to be completed at the time of study intervention discontinuation are included in the schedule of assessments in *section 13.1*.

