9.2.2 Reporting of UADE

Site Reporting Requirements

- The study investigator shall complete an Unanticipated Adverse Device Effect
 Form and submit to the UVA CC and to the reviewing Institutional Review Board
 (IRB) according to the IRB's guidelines, but in no event later than 10 working days
 after the investigator first learns of the effect.
- Non relying sites: report to your IRB in accordance with your IRB guidelines.
- Relying sites (use the UVA IRB-HSR as the IRB of record): report to the UVA CC within 5 calendar days so that the UVA CC can report to the reviewing IRB within 10 calendar days.
- UVA site: report to the UVA CC within 5 calendar days so that the UVA CC can report to the reviewing IRB within 10 calendar days.

UVA Reporting Guidelines

 The UVA CC is responsible for conducting an evaluation of an unanticipated adverse device effect and shall report the results of such evaluation to all reviewing IRBs and participating investigators within 10 working days after the UVA CC first receives notice of the effect. Thereafter, the UVA CC shall submit such additional reports concerning the effect as the IRBs/participating investigator requests.

Version Date: 11/16/2021

- If the PI or UVA DSMC determine that an unanticipated adverse device effect
 presents an unreasonable risk to subjects shall terminate all investigations or
 parts of investigations presenting the risk as soon as possible. Termination shall
 occur not later than 5 working days after the sponsor makes this determination
 and not later than 15 working days after the UVA CC first received notice of the
 effect.
- For events considered at least possibly related to BrachyGel, notify Brachyfoam within 72 hours of UVA CC's awareness of the event. To do so, email [contact].

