10.5 Safety Monitoring

All study participants who receive treatment will be assessed for the occurrence of treatment related adverse events. Adverse events of potential concern related to the vaginal packing, are acute vaginal adverse events (aVAE) which: i) is determined to be at least possibly related to BrachyGel; ii) occurs within the first 30 days from 1st Brachytherapy treatment utilizing BrachyGel (ie. Period 2 or 3 depending on the randomization arm); and iii) meets the criterion below:

Has any of the following vaginal toxicities grade >= 3 according to CTCAE:

- Vaginal pain
- Vaginal perforation
- Vaginal hemorrhage
- Vaginal inflammation
- Vaginal infection
- Dyspareunia

Safety will be assessed by monitoring the number of participants who experience an aVAE. Results reported in Romano et al 2017 on high-dose brachytherapy experience at UVA noted that 0/74 = 0% (upper limit of 95% CI of 4.9%) patients experienced grade ≥3 aVAE.²⁰ Others have reported similarly low rates with at most 2% for late vaginal toxicity.^{21,22} For this study the upper boundary of a sequential probability ratio test (SPRT) based upon a binomial test of proportions for aVAE will be used for monitoring, to protect against excessive aVAE rates. The stopping boundary is for a SPRT contrasting a null 4% versus an unacceptable 9% aVAE rate, with nominal type I and II errors of 10% and 10%, respectively. The slope of the parallel line for monitoring is 2.54 and the intercept is 0.062.

Safety stopping guidelines for the occurrence of aVAEs are detailed in the following table. If a stopping bound is crossed then accrual to the study will be suspended until the study PI, co-investigators and the DSMC can review the data, and determine if the study should continue, be amended or be closed to further accrual.

| Number of participants who received BrachyGel | Number with grade ≥ 3 aVAE | | |
|---|----------------------------|--|--|
| 3-7 | ≥ 3 | | |
| 8-23 | ≥ 4 | | |
| 24-39 | ≥ 5 | | |
| 40-45 | ≥ 6 | | |

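### Crossing the vaginal-toxicity bound suspends only accrual; Section 10.5 should also hold already randomised women to standard packing until the review is done

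*Combined protocol and SAP*

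**What the plan says.** Section 10.5 counts participants with an acute vaginal adverse event (aVAE) that is at least possibly related to BrachyGel, falls within 30 days of first BrachyGel use, and meets this criterion: "Has any of the following vaginal toxicities grade >= 3 according to CTCAE". The consequence of crossing the bound is "If a stopping bound is crossed then accrual to the study will be suspended", pending review by the PI, co-investigators and DSMC, who then "determine if the study should continue, be amended or be closed to further accrual". No time limit is given for that review. Section 11.1.4 has the DSMC meeting monthly.

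The provisions for individual participants lie elsewhere:

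- **7.2** has one grade-based reason to stop study treatment: "Severe, CTCAE Grade ≥ 4 adverse event considered at least possibly related to the packing procedure". Its other adverse-event reason is "Participant is unable to receive further brachytherapy due to an adverse event or a change in status".
- **7.1** permits suspension or termination of the study for cause.
- **7.3** leaves management to judgement after a clinically significant finding: "the investigator or qualified designee will determine if any change in participant management is needed".
- **9.2.2** requires termination once an unanticipated adverse device effect (UADE) is judged an unreasonable risk. The limits are 5 working days from that determination and "not later than 15 working days after the UVA CC first received notice of the" effect.
- **9.3** requires new information relevant to willingness to continue to be discussed with participants. Where a new risk is not in the signed consent, a woman still on treatment is given an updated consent and asked whether she wishes to go on.

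Under 6.1, Arm A receives BrachyGel at fractions 3 and 5 and Arm B at fractions 2 and 4. The synopsis puts fractions "2-7 days apart, followed by a 30 day safety visit".

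**The concern.** The bound exists to detect harm from BrachyGel, yet its only automatic effect is on women not yet enrolled. Women already randomised stay scheduled for BrachyGel while the signal is under review. None of the provisions listed above is triggered by the bound, and none requires a change of packing because of it. Section 2.2.5 says the product has not been used in living humans. Section 11.4 says that an investigator who founded the manufacturer will administer about half of the UVA fractions. Both facts favour a rule fixed in advance over decisions made fraction by fraction.

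A safe default is at hand. Standard packing is the comparator, and every participant receives it at fraction 1 and at two later fractions, so a hold need not interrupt brachytherapy.

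Any hold, including a discretionary one, also raises an analysis question. Section 10.3.1 makes a participant evaluable after three fractions, whichever packing she received. A woman held before her period 1-2 BrachyGel fraction would have standard packing in both periods and would still enter the primary comparison. Such pairs carry no packing contrast and pull the estimated difference towards zero, which favours non-inferiority.

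**Working it through.** **1. Reproduce the bound.** Inputs from 10.5: p0 = 0.04, p1 = 0.09, both error rates 0.10. With OR = p1(1−p0)/[p0(1−p1)]:

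- intercept = ln(0.90/0.10)/ln(OR) = 2.542
- slope = ln[(1−p0)/(1−p1)]/ln(OR) = 0.0619

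Rounding up 2.542 + 0.0619n gives 3 for n = 3-7, 4 for 8-23, 5 for 24-39 and 6 for 40-45, which matches the table. (The text swaps the labels slope and intercept; the table is right.)

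**2. Chance of crossing.** Exact binomial recursion through the table to n = 45 gives 2.6% at a true rate of 4%, 31.5% at 9% and 76.4% at 15%.

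**3. Fractions outstanding at a crossing.** Uniform accrual is assumed: 57 participants over 14 months (synopsis and 10.4), so 57/14/30.4 = 0.134 per day, half to each arm. Let L be the days from randomisation to fraction 2 (0-10, from 6.4) and g the days between fractions (2-7). After randomisation, BrachyGel is due at L+g and L+3g in Arm A and at L and L+2g in Arm B.

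Fractions outstanding = 0.134 × (2L+3g):

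- L=0, g=2: 0.80
- L=5, g=4.5: 3.15
- L=10, g=7: 5.49

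**4. Fractions given before review ends.** For a review of d days, assuming nobody changes packing meanwhile, the number is (0.134/2) × Σ min(d, due time) over the four due times.

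| Review length | L=0, g=2 | L=5, g=4.5 | L=10, g=7 |
|---|---|---|---|
| 3 days | 0.067 × 8 = 0.54 | 0.067 × 12 = 0.80 | 0.067 × 12 = 0.80 |
| 7 days | 0.067 × 12 = 0.80 | 0.067 × 26 = 1.74 | 0.067 × 28 = 1.88 |
| 30 days | 0.067 × 12 = 0.80 | – | 0.067 × 81 = 5.4 |

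**5. Weight the 3-7 day range by the chance of crossing.**

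- At 9%: 0.54 × 0.315 = 0.17 to 1.88 × 0.315 = 0.59
- At 4%: 0.54 × 0.026 = 0.01 to 1.88 × 0.026 = 0.05

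**6. What a hold costs the primary comparison.** A period 1-2 pair is lost if the woman's first BrachyGel fraction is still due when the hold begins and passes before it is released. The maximum, if the hold outlasts all such fractions, is:

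- Arm A: 0.067 × (L+g) = 0.13 (L=0, g=2) to 1.14 (L=10, g=7)
- Arm B: 0.067 × L = 0 to 0.67
- Total: 0.13 to 1.81, or 0.3% to 4.5% of 40 evaluable

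The loss is larger in Arm A because its first BrachyGel fraction comes one interval later.

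**The case against.** The strongest case against is that the protocol already has ways to protect these women. Section 7.1 allows suspension and 7.3 allows a change of management. The statement of compliance permits deviation to remove an immediate hazard, and an amendment under 10.5 could include a packing hold. Section 9.3 speaks directly to women still on treatment and is mandatory where it applies. The UADE route is also wider than it may look: in Table 2 only vaginal perforation is expected at grade 3, so the other five aVAE terms are unexpected at that grade. The FDA regards the device as non-significant risk. All of this stands and keeps the point minor. It does not close the gap, because each provision needs a separate judgement or the woman's own refusal, and the UADE route also requires the effect to be serious.

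A reader might draw four stronger conclusions that the documents do not support:

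- **That every outstanding fraction would be given after a crossing.** Multiplying all outstanding fractions by the chance of crossing gives 0.25 to 1.73 at a 9% rate. That holds only if review takes about a month and nobody intervenes. Section 10.5 neither requires nor rules out such a wait.
- **That the 15-working-day UADE limit sets the pace.** It is about 21 calendar days, against 4 to 14 days between a woman's two BrachyGel exposures. But it is an outer limit: prompt action is required, and within 5 working days of the determination.
- **That grade 4 in 7.2 contradicts grade 3 in 10.5.** One governs permanent discontinuation of an individual and the other a trial-level signal, so different thresholds are legitimate.
- **That a woman with her own grade 3 aVAE must be moved to standard packing.** Table 1 calls gauze uncomfortable and slow to insert with forceps, and retractors difficult to place. Nothing shows that either is safer for an injured woman. That decision belongs to the clinician under 7.3.

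**Conclusion.** The point holds as a minor, cheap improvement. As written, crossing the bound stops new accrual but leaves randomised women scheduled for BrachyGel during a review with no deadline, unless a clinician, the PI, the DSMC or the woman decides otherwise. The expected reach is below one fraction for a review of 3 to 7 days, even at the rate the protocol calls unacceptable; after an actual crossing it is one or two fractions, and up to about five if review waits a month. These figures rest on uniform accrual, equal allocation, the stated ranges for spacing and randomisation lead time, assumed review lengths, and no change of packing in the meantime. The crossing probabilities run only to n = 45, where the table ends. The validity of the bound and of the trial is not in question.

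**What to change.** Add to 10.5:

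> From the time the bound is crossed until the PI/DSMC review releases the hold, remaining fractions of randomised participants use standard packing.

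Add to 10.3.1 or 10.6:

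> Participants who, because of a hold, received standard packing in both periods 1 and 2 do not count as BrachyGel contrasts in the primary non-inferiority comparison. They are reported separately by arm, and a sensitivity analysis includes them as randomised.

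The sensitivity analysis is needed because this is a post-randomisation exclusion that falls more on Arm A than on Arm B. Leave 7.2 at grade 4, and leave a woman's own grade 3 event to the clinician under 7.3.

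The cost is two short additions at the next amendment, with no change to the bound, the sample size or the procedures. Only if the bound is crossed are there further costs: the lost pairs computed above, set against 57 accrued for 40 evaluable; a few period 3-4 BrachyGel observations; and, for held women, packing that the protocol describes as less comfortable or harder to place.

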10.4 Sample Size and Accrual

For this crossover study the primary comparison is based upon the 2x2 initial crossover portion. The primary endpoint is the difference of D2cc dosimetry measurements between periods 1 and 2 (fractions 2 and 3) for sequence arm A and sequence arm B based upon a two-sample comparison of the mean difference to the non-inferiority margin. Data from 51 patients treated at UVA with fraction 2 and 3 information, reported overall in Romano et al 2018¹⁹, with standard packing resulted in a mean (standard deviation) of 0.12 (1.56) and 0.10 (0.92) D2cc for the difference for bladder and rectal dosimetry, respectively. The

width of the 95% CI for the mean difference was 0.9 and 0.5 for bladder and rectal dosimetry, respectively. Based upon these measurements and clinical judgement, a non-inferiority margin of δ =(0.12+1.56=1.68) was chosen for this study.

Version Date: 11/16/2021

Justification for the sample size is based upon obtaining sufficient accrual to test the primary hypothesis that use of the hydrogel vaginal packing is non-inferior to standard packing methods in 1) bladder and 2) rectal dosimetry by more than a non-inferiority margin. Let $diff_A$ and $diff_B$ denote the differences between fractions.

The primary hypothesis to be tested is H_o : μ_{diffA} - μ_{diffB} $\geq \delta$ versus H_a : μ_{diffA} - μ_{diffB} $< \delta$, where the non-inferiority margin, δ =1.68, *each* for bladder and rectal, with a one-sided 2.5% level t-test. A sample size of 20 evaluable cervical cancer participants per arm achieves 94% power to detect non-inferiority using a one-sided t-test when the margin of non-inferiority is 1.68, the true difference between the means and the reference (standard) value is 0.12, and the assume population standard deviation is 1.56. Power is 96% if one uses the estimates for rectal dosimetry.

Adjusting for participants not satisfying the evaluable criteria (*section 10.3.1*), it is estimated that approximately 57 cervical cancer participants will need to be accrued to the study in order to test the primary study hypothesis. Each site may allow up to 10 oncologist and 4 physicists/dosimetrist to participate in completing the Physician and Physicist Assessments.

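### The section 10.5 stopping table counts participants whose 30-day event window is still open, which modestly dilutes the observed rate and sometimes delays or misses a crossing

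*Combined protocol and SAP*

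**What the plan says.** Section 10.5 (Safety Monitoring) counts a vaginal toxicity as an aVAE if, among other criteria, it "occurs within the first 30 days from 1st Brachytherapy treatment utilizing BrachyGel". It then states: "Safety will be assessed by monitoring the number of participants who experience an aVAE". The boundary is the upper line of a binomial sequential probability ratio test (SPRT) "contrasting a null 4% versus an unacceptable 9% aVAE rate, with nominal type I and II errors of 10% and 10%, respectively". The first column of the stopping table is headed "Number of participants who received BrachyGel", and the table asks for 3, 4, 5 and 6 events at 3–7, 8–23, 24–39 and 40–45 participants. The consequence is stated as "If a stopping bound is crossed then accrual to the study will be suspended", pending review.

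No section requires a completed 30-day window before a participant is counted, and none says how a participant still inside the window is handled at a look. Section 11.1.4 has the data and safety monitoring committee (DSMC) meeting monthly. Section 10.4 says "approximately 57 cervical cancer participants will need to be accrued", and the synopsis says "Accrual should be completed within 14 months".

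**The concern.** A binomial SPRT takes one known outcome from each participant counted. Under the printed heading a participant enters the denominator on the day of first BrachyGel use, but can contribute an event for another 30 days. Until then she is scored as event-free. Near a step of the table this changes the action: 4 events among 20 known outcomes meets the bound, but with four more participants just treated the table is read at 24 and asks for 5.

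This is the only numerical stopping boundary for vaginal toxicity, for a product that section 2.2.5 says has not been used in living humans. Even with complete outcomes, the rule crosses in fewer than a third of trials at the rate the plan calls unacceptable, so there is little sensitivity to give away.

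**Working it through.** **1. The plan's boundary reproduces.** Inputs from section 10.5: p0 = 0.04, p1 = 0.09, both errors 0.10.
- Log odds ratio: ln[0.09 × 0.96 / (0.04 × 0.91)] = 0.8644.
- Intercept: ln(0.90/0.10) / 0.8644 = 2.1972 / 0.8644 = 2.542.
- Slope: ln(0.96/0.91) / 0.8644 = 0.0535 / 0.8644 = 0.0619.
- Boundary: 2.542 + 0.0619n, rounded up. The line is 2.97 at n = 7, 3.04 at 8, 3.97 at 23, 4.03 at 24, 4.96 at 39 and 5.02 at 40, which gives the printed rows exactly. (The text attaches the names slope and intercept to the wrong constants; that is a separate point.)

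**2. Open windows at a look.** Accrual is 57/14 = 4.07 a month. With a 30-day window, simulation gives a mean of about 3.9 open participants at a monthly look during accrual. Each raises the line by 0.062, so the shift is 3.9 × 0.062 = 0.24 of an event. With four open, the required count rises by one only when the closed count is 4–7, 20–23 or 36–39. At 42–45 closed, the entry falls beyond the last row.

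**3. Benchmark.** Exact recursion on the printed table to n = 45, checked after every participant with every outcome known, gives a crossing probability of 2.6% at a true 4% rate, 31.5% at 9%, 76.4% at 15% and 93.8% at 20%.

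**4. Effect of the open windows.** Simulation used 8,000 trials per scenario, Poisson accrual at 4.07 a month, monthly looks and the table to 45. The documents do not give event timing, so two assumptions were run: uniform over 30 days, and early (exponential, mean 7 days).

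| True rate | As written | Closed window or event | Closed windows only | Exact, all known |
|---|---|---|---|---|
| 4% | 1.8–2.0% | 2.6–3.1% | 2.2% | 2.6% |
| 9% | 23.9–26.7% | 31.2–34.9% | 27.4–28.5% | 31.5% |
| 20% | 89.3–91.1% | 93.7–94.7% | 91.8–92.4% | 93.8% |

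Ranges run from uniform to early timing. A further simulation put the closed-or-event figure at 9% as high as 36%.

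The 9% shortfall against the exact figure is 31.5 − 26.7 = 4.8 to 31.5 − 23.9 = 7.6 points. Not all of it is dilution. The closed-only column has no open windows, yet monthly looks alone bring it to 27.4–28.5%. Against that column the loss is 28.5 − 26.7 = 1.8 to 27.4 − 23.9 = 3.5 points.

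**5. Continuous looks, 9% rate.** As written, crossing is 27.3–30.7% across uniform, mean-7-day and mean-2-day timing. That is 31.5 − 30.7 = 0.8 to 31.5 − 27.3 = 4.2 points below the exact figure. The closed-or-event count gives about 35–39%.

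**6. When crossings happen (9%, uniform timing, monthly looks).** Under the closed-or-event count 31.2% of trials cross. The table as written crosses at the same look in 18.9% of all trials, later in 5.1% and never in 7.3%. So 18.9/31.2 = 61% of those crossings are unaffected.

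**7. Sensitivity.** At 45/14 = 3.21 a month, crossing at 9% is 26.7–27.5% as written and 32.6–33.8% with closed-or-event. At an assumed 8 a month (uniform timing) it is about 17% against 33%. If the table ran to 57, the figures at the planned pace would be 35.9–37.6% and 41.3–43.2%, against 42% exact.

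**The case against.** A reader might infer that the table as written generally stops late or not at all. The documents do not support that. Most crossings fall at the same look. A rule that waits for closed windows before counting either events or non-events is often slower: as written, the table crosses earlier than that rule in 11.3% of trials and later or never in 2.1% + 3.5% = 5.6% (9%, uniform timing).

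The closed-or-event count is also a generous comparator. Events enter its denominator at once while non-events wait 30 days, so it over-reads the rate. With continuous looks it crosses in about 35–39% of trials at 9%, above the exact 31.5%. It should not be presented as the SPRT the plan designed, and its gap over the printed rule overstates the dilution. This stands, and it is why the benchmark here is the exact figure.

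Timing matters too. Section 2.3.1 expects packing pain to resolve within a day, so early events are plausible, and early timing shrinks the loss.

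Finally, crossing only suspends accrual for review. Monthly DSMC review of all adverse events (11.1.4), 24-hour reporting of serious events (9.1.7), the device-effect provisions (9.2.2) and suspension for unacceptable risk (7.1) all remain. A cluster just under a bound would still be seen. This limits the consequence, but it does not make the denominator right: the heading states a rule, and that rule scores unknown outcomes as non-events.

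**Conclusion.** The point holds as a modest defect. The stated denominator includes participants with open windows, which dilutes the observed rate and sometimes delays or loses a crossing. At planned accrual, monthly looks and a true 9% rate, the chance of crossing is about 24–27% as written, against 31.5% for the printed table with all outcomes known. Part of that difference is due to look spacing. With continuous looks the loss is about 0–4 points. These figures rest on the planned pace of 57 in 14 months, on the table ending at 45, and on assumed uniform or early event timing. The loss grows if accrual is faster. It does not show that the safety rule fails in general; it supports an inexpensive correction that favours safety.

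**What to change.** In section 10.5, relabel the first column of the stopping table: *Number of participants who have completed 30 days from first BrachyGel use or have had an aVAE*. Keep the bounds, count events as soon as they are known, and say that other participants still inside the window are left out at that look.

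State the operating characteristics of the relabelled rule. With monthly looks these are about 31–36% crossing at 9% and about 3% at 4%. With continuous looks they are about 35–39% at 9% and up to about 4% at 4%.

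The cost is one column heading, a sentence in section 10.5 and a line in the DSMC report. There are two downsides to disclose. The false-stop rate at 4% rises by about one point, from about 2% to about 3%, still far below the nominal 10%. And the rule crosses slightly more often than the exact SPRT, because events enter the denominator before non-events.
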